4.5 Selection of Clinical Sites/Labs

This single center study will be performed at the Emory University Hospital/Emory Transplant Center (ETC). The ETC and our team of investigators has extensive experience and a well-established infrastructure to support the proposed clinical research program. Emory investigators played a lead role in the design, conduct, analysis and interpretation of all phases of the preclinical and clinical development for belatacept, achieving high enrollment in the Phase 2 and 3 studies and maintaining follow-up of subjects for >10 years. Emory is the highest enrolling site (540 patients) in an FDA-mandated post-approval safety study (ENLIST). We have conducted many investigator-initiated studies including trials of alemtuzumab (Campath®) induction with belatacept, randomized trials of q 1 vs q2 month maintenance and belatacept vs conventional management to inhibit sensitization in patients with failing allografts. Further, Emory has conducted research in the NIH consortia (including the Immune Tolerance Network, Clinical Islet Transplantation Study, and Clinical Trials in Organ Transplantation). Emory has well-developed infrastructure to support mechanistic studies having served as a Core in NIH and industry-sponsored trials for flow cytometry and donor-specific antibody assessment.

The ETC is a large volume clinical transplant center performing in excess of 350 kidney transplants each year. When the inclusion and exclusion criteria were applied retrospectively to kidney transplants performed in a recent three-year period (2014-2016) the number of eligible candidates ranged from 105-133.

5 Known and Potential Risks and Benefits to Participants

5.1 Risks of Investigational Product or Intervention as cited in Investigator Brochure or Package Insert

Risks of Abatacept

The package insert for abatacept (ORENCIA®, Bristol Myers Squibb) lists the following adverse effects:⁵ Most common adverse events ($\geq 10\%$) are headache, upper respiratory tract infection, nasopharyngitis, and nausea.

- Serious infection, including sepsis and pneumonia, have been reported in patients treated with the intravenous form of abatacept. Some of these infections have been fatal.
- Serious infections have occurred in patients on concomitant immunosuppressive therapy which in addition to their underlying disease could further predispose them to infection.
- Hypersensitivity observed in $<0.1\%$ of patients treated with the intravenous form of the abatacept. Other reactions potentially associated with drug hypersensitivity, such as hypotension, urticaria, and dyspnea, each occurred in less than 0.9% of treated patients.
- May blunt effectiveness of immunizations.

5.2 Risks of Investigational Product or Intervention cited in Medical Literature

None

5.3 Risks of Other Protocol Specified Medications

5.3.1. Risks of Tacrolimus

Side effects of tacrolimus include hypertension, glucose intolerance, peripheral neuropathy, renal insufficiency, abnormal liver function studies, seizures, nausea, vomiting, confusion, hypomagnesaemia, tremulousness, neurotoxicity, posterior reversible encephalopathy syndrome (PRES), progressive multifocal leukoencephalopathy (PML), interstitial lung disease, BK nephropathy, and increased risk of secondary malignancies. Additional information about tacrolimus can be found in the package insert.

5.3.2. Risks of Maintenance Immunosuppressive Medications

Administration of all immunosuppressive and immunomodulatory therapies used presently to prevent rejection of transplanted tissues carry general risks of opportunistic infection and malignancy, including lymphoma ($\sim 1\%$), and skin cancers. These agents are not recommended for nursing mothers, and it is recommended (and mandated in the current protocol) that women of childbearing potential (WOCBP) use effective contraception throughout the study. For men, the effect of the study drug on sperm is not known. To protect against possible side effects, men should take precautions to prevent pregnancy in all sexual partners while taking the study drug and for 30 days after the last dose. Male subjects and the study doctor will discuss method of birth control to use throughout the study. We intend to monitor for the occurrence of infections and malignancy as described above and will implement appropriate treatment options as necessary.

5.3.3. Risks of Prednisone

Adverse effects of corticosteroid therapy associated with short-term therapy have included sodium retention-related weight gain and fluid accumulation, hyperglycemia and glucose intolerance, hypokalemia, gastrointestinal upset and ulceration, reversible depression of the hypothalamic-pituitary-

adrenal (HPA) axis, and mood changes ranging from mild euphoria and insomnia to nervousness, restlessness, mania, catatonia, depression, delusions, hallucinations, and violent behavior. Long-term use of prednisone may be associated with hypertension, hyperlipidemia, weight gain with Cushingoid features, osteopenia, and skin changes including acne and easy bruisability. We intend to monitor for the occurrence of corticosteroid side-effects and will implement appropriate treatment options as necessary.

5.3.4. Risks of Mycophenolate Acid Derivative (Mycophenolate Mofetil/MMF or enteric coated Mycophenolic Acid/MPA)

Mycophenolate mofetil (MMF) and enteric-coated mycophenolate sodium are approved (in combination with cyclosporine and corticosteroids) as immunosuppressive agents for renal, cardiac, and hepatic solid organ transplantation. Adverse events reported in > 30% of renal, cardiac or liver transplant patients receiving MMF were pain, fever, headache, asthenia, anemia, leukopenia, thrombocytopenia, leukocytosis, urinary tract infection, hypertension, hypotension, peripheral edema, hypercholesterolemia, hypokalemia, hyperglycemia, increased creatinine and BUN, cough, hypomagnesaemia, diarrhea, constipation, nausea, vomiting, respiratory infection, dyspnea, lung disorder, pleural effusion, tremor and insomnia. The side effect profile of enteric-coated mycophenolate sodium is similar to those of MMF.

There is an increased risk of developing lymphomas and other malignancies, particularly of the skin. Lymphoproliferative disease or lymphoma developed in 0.4% to 1% of patients receiving MMF 1000 - 1500 mg twice daily. Severe neutropenia developed in up to 2% of renal transplant recipients receiving MMF 1500 mg twice daily. MMF can cause fetal harm (including spontaneous abortion in the first trimester and can cause congenital malformations in the offspring of women who are treated during pregnancy) when administered to a pregnant woman. Cases of progressive multifocal leukoencephalopathy (PML), sometimes fatal and pure red cell aplasia have been reported in patients treated with MMF. Gastrointestinal bleeding (requiring hospitalization) has been observed in approximately 3% of renal, in 1.7% of cardiac, and in 5.4% of hepatic transplant patients treated with MMF 1500 mg twice daily. Additional information about MMF can be found in the package insert. Follow up as specified in the SOE will allow detection of the adverse events specified above. Management of mycophenolate associated adverse events will include dose reduction, conversion to MPA or azathioprine, or discontinuation of MMF.

5.4 Risks of Study Procedures

5.4.1. Kidney Transplant Rejection

All recipients of kidney transplants (except for transplant from identical twins) are at risk for rejection. Most rejection episodes are reversible with additional immunosuppression. All enrolled subjects shall be stringently monitored for empirically treated rejection, biopsy proven acute T cell mediated rejection, and biopsy proven active antibody mediated rejection episodes.

5.4.2. Blood Draws

The amount of blood that may be drawn from adult subjects for research purposes will not exceed 10.5 mL/kg or 550 mL, whichever is smaller, over an eight-week period. All blood samples for the mechanistic study will be obtained at the time of scheduled blood draws, so there will be minimal additional risk associated with obtaining the study samples.

The subject may experience some discomfort at the site of the needle entry, bruising, swelling, redness, fainting, or local infection. The additional amount of blood could contribute to the development of anemia. The subject's clinical condition will be taken into consideration to determine if research blood tests can be performed.

5.4.3. Risks of Coronavirus Disease 2019 (COVID-19)

Early reports indicate an increased risk of critical illness and mortality in kidney transplant recipients infected with SARS-CoV-2, possibly due to chronic immunosuppression and co-existing conditions.^{95,96} Given that both immunosuppressive agents including abatacept, mycophenylate mofetil, tacrolimus, and prednisone are associated with increased risk of infection in general, it is possible that study therapy may increase the risk of developing symptomatic severe COVID-19 illness in subjects who would have otherwise been asymptomatic. To limit this risk, potential participants must have received a primary series of COVID-19 vaccination and the most recent recommended booster available prior to transplantation.

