	
 8. Female study participants of childbearing potential must have a negative pregnancy test on Day 0 prior to receiving the first dose of study drug . 9. Agreement to use contraception; according to the FDA Office of Women's Health (http://www.fda.gov/birthcontrol), there are a number of birth control methods that are more than 80% effective. Female study participants of child-bearing potential and men must consult with their physician and determine the most suitable method(s) from this list to be used from the time that study treatment begins until after study completion- 10. Vaccines up to date as per DAIT guidance for patients in transplant trials. (Refer to Appendix 2: DAIT Vaccine Guidance for Patients in Interventional Adult Transplant Trials) 11. Study participants must have a negative purified protein derivative (PPD) or negative testing for tuberculosis using an approved IGRA blood test, such as QuantiFERON®-Gold TB or T-SPOT-TB assay. PPD or IGRA testing must be documented to have been performed within the 52 weeks before enrollment. Patients with latent TB may become eligible according to local or national guidelines following completion of treatment.

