4.2 Enrollment

The study team will approach potential enrollees shortly after transplantation. Study staff will provide information about the trial including the consent form, to interested patients.

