4.3 Inclusion Criteria

Individuals who meet all of the following criteria are eligible for enrollment as study participants:

1. Must be able to understand and provide informed consent.
2. Male or Female, 18-70 years of age at the time of enrollment (all races and ethnicities).
3. Negative crossmatch (virtual or physical) at time of transplant.
4. First dose of Study Drug must be given no less than 8 weeks, no more than 20 weeks post-transplant.
5. First time renal transplant who has been treated with belatacept from the time of transplant, receiving tacrolimus (target trough 3-5 ng/ml), mycophenylate mofetil (or mycophenolic acid or azathioprine), prednisone (also see exclusion criteria).
6. eGFR ≥ 40 ml/min/m² (using 2021 CKD-EPI equation).
7. Must have prior documented evidence of EBV seropositivity.
8. Female study participants of childbearing potential must have a negative pregnancy test on Day 0 prior to receiving the first dose of study drug.
9. Agreement to use contraception; according to the FDA Office of Women's Health (<http://www.fda.gov/birthcontrol>), there are a number of birth control methods that are more than 80% effective. Female study participants of child-bearing potential and men must consult with their physician and determine the most suitable method(s) from this list to be used from the time that study treatment begins until after study completion.
10. Vaccines up to date as per DAIT guidance for patients in transplant trials. (Refer to Appendix 2: DAIT Vaccine Guidance for Patients in Interventional Adult Transplant Trials)

11. Study participants must have a negative purified protein derivative (PPD) or negative testing for tuberculosis using an approved IGRA blood test, such as QuantiFERON®-Gold TB or T-SPOT-TB assay. PPD or IGRA testing must be documented to have been performed within the 52 weeks before enrollment. Patients with latent TB may become eligible according to local or national guidelines following completion of treatment.

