Zoster (VZV)	
To be eligible, the pre-transplant enrollee must have prior to transplant:
 
 • IF >19 years of age: at least one dose of Shingrix vaccine (RZV: Zoster Recombinant, which is NOT a live vaccine); if both doses of Shingrix are not completed prior to transplant, enrollees will be expected to complete the series after transplant 
NOTE: Hemodynamically unstable heart transplant candidates and ventilated lung transplant candidates, or post-transplant study enrollees can receive their first dose of the Shingrix vaccine once they are stable, post-transplant.
 
In January 2022, CDC modified the age recommendation from ≥ 50 years of age to ≥ 19 years of age. To allow time for adoption of this new recommendation, the criteria above for individuals between 19 and 49 years of age (inclusive) will be effective for DAIT studies starting January 1, 2023. If a subject is enrolled prior to 19 years of age, the Shingrix vaccine is recommended once they reach their 19th birthday.

MMR	
To be eligible, the enrollee must have prior to transplant [MMR is a live vaccine¹, contraindicated after transplant]:
 
 • Documentation that they have received MMR-containing vaccine, or • Documentation of Measles titers (IgG, do not test for IgM) 
NOTE: Documentation of titers to Mumps or Rubella is NOT required.

COVID-19	Completion of a primary COVID-19 vaccination series with a Health Authority-approved or authorized vaccine; (e.g., FDA in US or Health Canada) is an eligibility requirement for all DAIT/NIAID Transplantation Branch Clinical Trials.
-----------------	-----------------------------------------------------------------------------------------------------------------------------------------------------------------------------------------------------------------------------------------

Version 9.0 05-08-2022

Unless otherwise specified, “documentation” means the vaccine in question is recorded in a formal medical record, military record, school record, state or local vaccine registry, or official vaccination card.

¹ It is usual to postpone transplantation for 4 weeks after receipt of the live attenuated MMR or Varicella (Chickenpox) vaccines; if vaccination is not possible, the patient **cannot be enrolled** in this investigational drug (IND) study.

Reference: <https://www.cdc.gov/vaccines/schedules/downloads/adult/adult-combined-schedule.pdf>

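### Section 5.4.3 requires a COVID-19 booster as a safety measure, but the eligibility criteria, through Appendix 2, require only the primary series

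*Combined protocol and SAP*

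**What the plan says.** Section 5.4.3 notes early reports of more critical illness and death in infected kidney recipients, and allows that study therapy may raise the risk of severe disease. As the step that limits this risk, it says that potential participants "must have received a primary series of COVID-19 vaccination and the most recent recommended booster available prior to transplantation".

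Inclusion criterion 10, worded alike in the synopsis and section 4.3, reads "Vaccines up to date as per DAIT guidance for patients in transplant trials" and adds a pointer: "Refer to Appendix 2: DAIT Vaccine Guidance for Patients in Interventional Adult Transplant Trials". The COVID-19 row of Appendix 2 reads "Completion of a primary COVID-19 vaccination series with a Health Authority-approved or authorized vaccine" and says that this "is an eligibility requirement for all DAIT/NIAID Transplantation Branch Clinical Trials". It does not mention a booster.

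Section 4.3 opens with the rule that decides entry: "Individuals who meet all of the following criteria are eligible for enrollment as study participants". Section 9.1 adds a last check of the eligibility criteria just before enrolment and the start of treatment.

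**The concern.** Section 5.4.3 is worded as a condition on who may join the study and is offered as the mitigation for a named risk. A condition of that kind belongs in the list that screening staff apply, and the booster is not there. Staff who follow section 4.3 faithfully have no prompt to check it.

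What is at stake is a stated protection that screening may not deliver. Participants take abatacept with tacrolimus, mycophenolate or azathioprine, and prednisone, and section 13.9 lists COVID-19 among the serious infections of interest. Anyone relying on section 5.4.3, including the ethics board and the DSMB, would believe that every participant for whom a booster was available had received it. The same patient could also be called eligible by one reader and wrongly enrolled by another.

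**Working it through.** No figure in the plan depends on this point, so the check is a comparison of texts.

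**Step 1: what each text requires.**

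| Text | Primary series | Booster |
|---|---|---|
| Section 5.4.3 | required | required, if a recommended one was available before transplantation |
| Criterion 10 with Appendix 2, COVID-19 row | required | not mentioned |

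**Step 2: whether another criterion supplies the booster.** None of the other 10 inclusion criteria concerns COVID-19 vaccination. None of the 19 exclusions in section 4.4 names it. The other Appendix 2 rows cover hepatitis B, influenza, pneumococcus, varicella, zoster and MMR. Exclusion 1 (compliance with the protocol) and exclusion 7 (added risk in the investigator's opinion) are general and do not direct anyone to check booster status.

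**Step 3: apply both texts to each kind of patient**, supposing that all other criteria are met.

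| Patient | Eligible under 4.3 and 4.4 | Meets 5.4.3 |
|---|---|---|
| No primary series | no | no |
| Primary series, and the latest recommended booster | yes | yes |
| Primary series, no booster, and none recommended and available before transplantation | yes | yes |
| Primary series, no booster, although one was recommended and available before transplantation | **yes** | **no** |

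Only the last row gives different answers. That is the whole extent of the inconsistency.

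**Step 4: room for a stricter rule.** Section 4.5 reports 105 to 133 eligible candidates when the criteria were applied to transplants from 2014 to 2016, against 18 participants needed: 105 / 18 = 5.8 and 133 / 18 = 7.4. These counts predate COVID-19 and say nothing about booster uptake or willingness to take part. They show only that losing some candidates is unlikely to be critical.

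**The case against.** **The texts are compatible.** Appendix 2 states one requirement without claiming to be exhaustive, section 5.4.3 is merely stricter, and a site that follows the whole protocol meets both. This stands as far as it goes: a reader might infer a flat contradiction, and there is none. But section 4.3 makes its own list sufficient for eligibility, so the stricter rule can be missed by someone who applies that list correctly.

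**Up-to-date vaccination implies boosters.** Criterion 10 ties that phrase to the DAIT guidance, and the guidance in Appendix 2 names only the primary series.

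**Section 5.4.3 may be carried-over text.** It cites references 95 and 96, while the reference list has six entries. This suggests borrowed wording without proving it. It does not remove the mismatch, but it is a good reason not to assume that the booster rule is the intended one.

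**A stronger reading on timing.** Since "The study team will approach potential enrollees shortly after transplantation" and "First dose of Study Drug must be given no less than 8 weeks, no more than 20 weeks post-transplant", a reader might infer that section 5.4.3 sets a deadline that has already passed for every candidate, that this is a defect in itself, and that catch-up should be allowed until the first abatacept dose. The documents do not support that. No text offers the first dose as a booster deadline, and under section 9.2 enrolment occurs at consent. Conditions fixed at or before transplantation are ordinary here: the crossmatch (criterion 3), belatacept from transplantation (criterion 5), and the varicella and MMR rows of Appendix 2. Those two are live vaccines and so not exact parallels, but they show that a pre-transplant vaccine condition is not anomalous.

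**Conclusion.** The inconsistency is real and minor. It affects one kind of patient: primary series complete, no booster, and a recommended booster available before transplantation. A reader might infer that every patient without a booster breaches section 5.4.3; the wording does not support that, because it asks only for a booster that was available by then.

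The number of such patients is unknown, and none is assumed. Everyone enrolled under either text has the primary series, and exclusion 7 lets the investigator turn away a patient thought to be at added risk. Sample size, endpoints and analyses are untouched.

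The conclusion assumes that section 5.4.3 means what it says when it sets a condition on potential participants. If it was meant only as background, the mismatch remains and the correction belongs in that section. It is worth correcting because two stated rules give different answers for the same patient and the repair is a single clause.

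**What to change.** Make the two texts agree. The choice is the sponsor's.

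- **If the booster is intended:** add a clause to criterion 10, in the synopsis and in section 4.3, requiring the booster in the terms of section 5.4.3 and cross-referring to it. Criterion 10 is the right place, since Appendix 2 is general guidance for all of the funder's transplant trials. This keeps the stated protection. It may exclude a few candidates; the documents do not allow that loss to be sized, but the pool in section 4.5 suggests that it is affordable.
- **If it is not intended:** remove the booster from section 5.4.3 so that it matches Appendix 2. This excludes no one, but gives up a protection that the protocol now states.

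Either way the cost is one clause in a protocol amendment, with no change to the statistical plan.

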5.5 Electronic Data Systems

It is possible that computer/data management systems could be maliciously attacked and personal identifiable information as well as other study documents compromised. There is also the potential of accidental loss of privacy during the consenting and enrollment process. To minimize or prevent this from happening, standard procedures such as using coded forms, locked files, and password protected, encrypted databases will be employed. Investigators and the appropriate study team members will complete training courses in secure data management/privacy. Finally, the Emory University data systems are fully compliant with Federal regulations and have up-to-date virus and malware protection.

5.6 Potential Benefits

This study might not provide direct or immediate benefit to study participants.

In general participants in clinical trials have more intensive follow-up than patients not enrolled in clinical trials, and this may be beneficial independent of study intervention.

6. Investigational Agent /Intervention

6.1 Investigational Agents: / Abatacept (ORENCIA®, Bristol Myers Squibb)

6.1.1. Formulation, Packaging, and Labeling

ORENCIA® (abatacept) ClickJect™ autoinjector is for subcutaneous administration and is clear to slightly opalescent, colorless to pale yellow solutions for subcutaneous administration.

ORENCIA® (abatacept) ClickJect™ autoinjector has a concentration of 125 mg/mL and is supplied as a single-dose disposable prefilled ClickJect autoinjector. The Type I glass syringe contained in the autoinjector has a coated stopper and fixed stainless steel needle (5 bevel, 27-gauge special thin wall, -inch needle) covered with a rigid needle shield. The autoinjector provides 125 mg of abatacept in 1 mL and is provided in a pack of 4 autoinjectors.

